#### Follow-up (6 weeks postpartum):

The primary endpoint will be assessed at six weeks postpartum (with flexibility for -1 week and +4 week window if needed because of scheduling reasons). Women returning for their routine 6-week postpartum visit will be asked to undergo a final follow-up assessment conducted by the Assessment Team, who will be masked to the allocation status of trial participants. Women in the biological substudy will also have a blood draw (using same techniques described above under 'baseline visit'). We will also administer the *Ages & Stages Questionnaire, Third Edition (ASQ-3)* to the infants of all participants in the trial to assess infant neurobehavioral functioning.

For the detailed description of the outcomes and time points, see **Table 4** below.

In the chart below, data collection procedures that are specific to the substudy are marked as Os in the chart instead of as Xs.

Table 4: Schedule of study assessment activities

	Screening	Baseline *	2 nd trimester	3 rd trimester**	Birth	6 weeks postpartum **
	Time 1	Time 2	Time 3	Time 4	Time 5	Time 6
Informed Consent	X	X				
Eligibility assessment						
Screening step 1 (age, residence, stage of pregnancy, language)	X					
Screening Step 2 (medical exclusions)	X					
Screening Step 3 (HADS anxiety inclusion)	X					
Screening Step 4 (SCID MDE exclusion)	X					
Assessments						
Socio-demographic questions		X				
PSS-10 (stress)				X		X
PES-Brief (pregnancy anxiety)		X		X		
PHQ-9 (depressive symptoms)						X
HADS (anxiety symptoms)	X	O	O			X
HADS (symptoms of depression)	X	O	O			X
MDE diagnosis (from SCID)	X					X
MSPSS (social support)	X		X			X
MRQ (relationships)	X		X			X
Empowerment	X					X
WHO-DAS (disability)	X		X			X
DHS IPV items (violence)						X
IPV Screening Question		X		X		(in the DHS module)
PAAS (behavioral activation)		X		X		X
Breastfeeding					X	X
Parenting self-efficacy						X
PBQ (bonding)						X
MIRI (maternal responsiveness)						X
MSEQ (maternal self-efficacy)						X
Anthropometry§§						X
Economic Data						
CSRI				X		X
Blood Draw (for biology aims)	O	O	O			O
Ages & Stages Questionnaire, Third Edition (ASQ-3)						O
From medical records						
Fetal outcome: SGA in utero*				X		
Pregnancy conditions:				X		
Birth outcomes: SGA, PTB, LBW					X	
Medications	X			X		X
Pregnancy conditions: medical status in pregnancy (e.g. pre-eclampsia, gestational diabetes)	X			X	X	X
Adverse event review					AT ALL TIMES	

\*Baseline assessment may be the same day or up to two weeks after screening.

Note: Full descriptions of the assessment tools are given in section 8.2.3.

\*\*Assessments will be somewhat flexible; the 6-week postpartum visit can be done a week early and up to three weeks after the 6 week mark (if scheduling issues preclude collecting data exactly at the desired time)

§This screener will be administered in order to be able to refer women with IPV to counseling, since it is considered an adverse event.

§§Anthropometry will be measured either our team or a healthcare provider at the 6 week postpartum visit.

[figure not shown]
2. Describe the number and type of study visits and/or contacts between the study team and the participant, how long they will last, and where/how they will take place.

For the assessments there will be a screening visit at the time of enrollment, visit at baseline (either at the same time if the woman is ready to enrol or within 2 weeks afterwards if she would like more time to think about it), in late pregnancy, at delivery, and at 6 weeks postpartum. See above for assessments that will be done at each visit. We expect baseline and the 6 week postpartum visits to last between 1 to 1.5 hours. We expect the 3rd trimester visit to be shorter, around 45 minutes. We expect the birth visit to only entail 5 minutes of data collection with the women, while the rest will be gathered from medical records.

For women randomized to the intervention, there will be 6 core intervention sessions and up to 2-6 booster sessions (depending on the time of enrolment). The first five core sessions will be delivered weekly as early in the pregnancy as possible, then the booster sessions will occur, with one final core session (Core Session 6) in the 3rd trimester. Booster sessions will be scheduled on a case by case basis, depending on the recruitment time of the pregnant mother. Please see Table 2 above for an outline of session content.

For women in the biological substudy, there will be an additional visit at 24 weeks gestation for a blood draw and HADS administration. See the Figure below for a timeline of study visits.

Figure: Timeline for participants in the intervention and control arms of the main trial

All assessments will be in the hospital, and we will attempt to pair them with her regular prenatal and postnatal medical visits when possible.

3. Describe the expected duration of the study from the perspective of the individual participant and duration overall.

Sessions will last between 45 minutes and an hour, and data collection will extend from the time of enrolment in early pregnancy ( $\leq 22$  weeks gestation) until the 6 week postpartum-end-point assessment.

Those who are randomized to the intervention arm will additionally experience the intervention. Please see Tables 1 and 2 for an outline of sessions for intervention and control participants, respectively.

4. Provide a brief data analysis plan and a description of variables to be derived.

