### **III. Study Design:**

- A. Provide an overview of your study design and methods. The study design must relate to your stated aims/objectives. Details will be requested later. If your study also involves analysis of existing data, please complete Section XI, "Secondary Data Analysis of Existing Data" in the last part of this research plan. If your study ONLY involves analysis of existing data, please use the research plan template for secondary data analysis (JHSPH IRB Research Plan for Secondary Data Analysis of Existing Data/Specimens).

A phase 3, two-arm, single-blind, individual randomized clinical trial will be conducted in the outpatient department of Holy Family Hospital (HFH) in Rawalpindi, Pakistan, to evaluate the impact of the HMHB intervention on the prevalence of CMDs at six weeks postpartum. We will enroll 1200 eligible women, individually randomizing them to either the intervention (i.e., HMHB) or control (i.e., routine care with similar frequency/timing of visits). Each woman randomized into the HMHB intervention arm will be assigned to a HMHB non-specialist provider who will deliver six individual and between two and six booster sessions of the HMHB intervention program. Women allocated to the control condition will receive routine care, but with increased contact so that frequency of contact will match between the study arms. The primary endpoint is the combined prevalence of GAD and MDE at six weeks postpartum. Data on outcome measures will be collected at birth, and at six weeks postpartum by a trained assessment team masked to the allocation status of the study participant (single-blind). All analyses will use an intent-to-treat (ITT) approach, using all subjects randomly assigned to intervention or control groups. We will also evaluate mediators and moderators of the intervention as well as the cost-effectiveness of the HMHB intervention compared with control arm.

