#### **IV. Participants:**

Describe the study participants and the population from which they will be drawn. Specify the inclusion and exclusion criteria. If you plan to include children, note their ages and whether you will include children in foster care. Note if the participants are particularly vulnerable in terms of cognitive limitations, education, legal migration status, incarceration, poverty, or some combination of factors.

Pregnant women attending the outpatient Obstetrics Department of HFH for antenatal care will be approached to determine interest in screening for possible eligibility and participation in the study. Women expressing interest will be asked to provide **consent for screening**, because our screening procedures include a formal assessment using the Hospital and Anxiety Depression Scale (HADS) (see inclusion criteria #6) and the depression component of the Structured Clinical Interview for DSM-5 (SCID) (see exclusion criteria #1). Those providing consent to be screened, will be assessed for eligibility to the intervention and enhanced usual care groups using the below inclusion and exclusion criteria:

- **Inclusion Criteria:**

1. ability to understand Urdu
2.  $\leq 22$  weeks' gestation
3. age  $\geq 18$  years
4. residence  $\leq 20$  km of Holy Family Hospital
5. intent to reside in the study areas until the completion of the study
6. score  $\geq 8$  on the HADS anxiety

- **Exclusion Criteria:**

1. Current major a depressive episode (MDE on SCID) or life-threatening health conditions including e.g. active severe depression or suicidal ideation
2. Self-reported past or current significant learning disability
3. Self-reported past or current psychiatric disorder (e.g. bipolar disorder or schizophrenia) or psychiatric care (e.g. current use of anxiolytic drug and/or other psychotropic drug)
4. medical disorders or severe maternal morbidity that require inpatient management that would preclude participation (e.g. eclampsia, pre-eclampsia, and antepartum hemorrhage)
5. ICU admission (indicated by diagnosis not admitted only for assessment)

For the healthy control group, unique to the biological substudy, inclusion and exclusion criteria will be as above, except that participants must score  $< 8$  on the HADS anxiety.

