### **Screening Procedures:**

As described briefly above, we will first approach all women to establish if they are  $\geq 18$  years old, reside within  $\leq 20$  km of Holy Family Hospital, intend to reside in the study areas until the study is complete, and understand Urdu to the HMHB. If they fulfill these demographic criteria, we will invite them to be screened in a private area about other exclusion criteria (e.g. their psychiatric history, history of psychiatric medications and history of a learning disabilities (See 100 Eligibility Screening Master Form, in Surveys/Instruments/Questionnaires in the Miscellaneous Section). If they are not excluded on this basis, these pregnant women will be further screened for having mild to high levels of anxiety on the HADS score  $\geq 8$  for anxiety by the research team member. As one of our exclusion criteria is a diagnosis of depression, the Structured Clinical Interview DSM disorders (SCID) module for Depression will also be used as a screening tool to rule out women with this diagnosis among those with a HADS score  $\geq 8$  for depression.

**Consent for Study Participation:** Women who ultimately screen eligible, will then be invited to participate in the main study. The staff person will indicate that based on the results of the screening the woman is eligible to participate, and she will give the pregnant woman a copy of the main study consent form (See 002 - Consent for Study Participation) and will go over the consent form with the woman, answering any questions she may have about the study. The woman will be approached first if possible and will be able to ask any questions, and/or take time to make a decision about participating. Although we are not asking husbands or other family members for consent, if there are family members present and the woman wishes for them to be present during the consent process we will comply with her wishes. We will describe and explain the study to both the woman and any accompanying family/friends. Women can decide at this point of contact to participate, or they may choose to take some time to make their decision (up to 14 days). If the latter option (i.e. delayed decision), our staff member will request a phone number to follow up with the

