#### Analysis of Primary Efficacy Endpoint(s)

The primary outcome of the study is the prevalence of cases of CMDs (GAD and MDE) in both study arms. Diagnosed cases of both GAD and MDE will be assessed with the Structured Clinical Interview for DSM Disorders (SCID).

The intervention group (enrolled after being screened for subclinical or clinical levels of anxiety) will be compared with non-intervention controls (selected on the same criteria) to examine the effects of the intervention on development of CMDs. The primary analysis will involve comparing pre- to post- changes in cases of the mothers randomly assigned to the two conditions using Fisher's exact test. Primary analyses will be non-parametric tests, however sensitivity analyses will use parametric models such as linear and logistic regression to control for baseline values of the mothers' characteristics (132). Other sensitivity analyses may evaluate whether there was more of an effect among women who got the full intervention. Variable transformations (such as square root or log) will be utilized as appropriate to meet the model assumptions.

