#### Analysis of Secondary Efficacy Endpoint(s)

We will secondarily compare the intervention and control groups in terms of changes in CMD symptom scores, by measuring depressive symptoms with the 9-item Patient Health questionnaire (PHQ-9) and the HADS anxiety questionnaires. Other outcomes of interest, but not primary targets, include birth outcomes (SGA, LBW, and preterm birth), perceived stress (using the Perceived Stress Scale –PSS), pregnancy-related anxiety (using the Pregnancy Experience Scale PES-Brief), maternal functioning (using WHO-DAS), marital relationships (MacArthur Relationship Questionnaire), IPV, women's empowerment, maternal bonding, maternal responsiveness, child growth at 6 weeks postpartum, as well as initiation and exclusivity of breastfeeding (WHO measures). Pregnancy-related symptoms of anxiety (measured with the PES-Brief) will be assessed at baseline and in the 3rd trimester.

For secondary hypotheses, we will estimate the effects of the intervention using birth and follow-up (6 weeks postpartum) measures separately. Primary analyses will be non-parametric tests, however sensitivity analyses will use parametric models such as linear and logistic regression to control for baseline values of the mothers' characteristics (132). Variable transformations (such as square root or log) will be utilized as appropriate to meet the model assumptions. For primary and secondary endpoints, in all regression models the coefficient on the HMHB vs. non-HMHB (control group) indicator variable will be taken as the estimated effect.

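### Table 4 omits the SCID diagnosis of GAD that the primary endpoint needs at six weeks, and no baseline GAD diagnosis is described for the planned before-and-after comparison of cases

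*Combined protocol and SAP*

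**What the plan says.** Three places in the text define the endpoint, its timing and its instrument.

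- Section III. Study Design, part A: "The primary endpoint is the combined prevalence of GAD and MDE at six weeks postpartum".
- Section V, Follow-up (6 weeks postpartum): "The primary endpoint will be assessed at six weeks postpartum", with a visit window around that date.
- Section V, Analysis of Primary Efficacy Endpoint(s): "Diagnosed cases of both GAD and MDE will be assessed with the Structured Clinical Interview for DSM Disorders (SCID". The same section makes the primary analysis a Fisher's exact comparison of the change in cases from before to after the intervention.

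The follow-up text then refers the reader to Table 4 for the detail of outcomes and time points. The item on study visits that follows the table points back to it for what is done at each visit. In Table 4 the only SCID entries are the MDE exclusion step at screening and the row "MDE diagnosis (from SCID", marked at screening and at six weeks. No row carries a GAD diagnosis. The general anxiety row at six weeks is "HADS (anxiety symptoms".

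**The concern.** The schedule of assessments is what forms, interviewer training and visit checklists are normally built from. Here it disagrees with the endpoint definition on a component of the primary outcome. A team that followed the table alone would interview for MDE at six weeks and record anxiety only as a symptom score. A diagnosis not made at that visit cannot be reliably reconstructed afterwards.

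There is a linked gap at entry. The primary analysis compares change in cases, but no GAD diagnosis is described before randomisation. Exclusion criterion 1 removes women with current MDE, and the background section says women with high anxiety are included so that GAD can be treated as well as prevented. GAD is therefore the component for which a before-and-after change would carry information, and it is the one with no stated starting value.

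**Working it through.** **Step 1. Set the text beside the table.**

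| Item | Text | Table 4 |
|---|---|---|
| MDE by SCID at six weeks | Required | Row present, marked at six weeks |
| GAD by SCID at six weeks | Required | No row |
| MDE by SCID before randomisation | Screening exclusion | Marked at screening |
| GAD by SCID before randomisation | Not described, but implied by a change-in-cases analysis | No row |

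**Step 2. Can another row stand in for GAD?** The HADS anxiety row is marked at six weeks, but the HADS yields a symptom score. The plan uses it under Analysis of Secondary Efficacy Endpoint(s): "We will secondarily compare the intervention and control groups in terms of changes in CMD symptom scores". PES-Brief measures pregnancy anxiety and is not marked at six weeks. Nor does the MDE row naturally cover both disorders: for the HADS, which also serves two conditions, the table gives anxiety and depression separate rows.

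**Step 3. Is the change in cases computable?** For each arm, change = cases at six weeks minus cases at entry.

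- MDE: women with current MDE are excluded, so entry cases are 0 by design, and the change equals six-week MDE cases.
- GAD: entry cases are not described as measured, so the change cannot be calculated from the scheduled data.

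A comparison of six-week prevalence between randomised arms needs no entry diagnosis, and it is what the primary objective in Section I states.

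**Step 4. What the sample size assumed.** Section III, part B gives a 30% CMD prevalence, a 30% relative reduction (0.30 × 0.70 = 0.21), 85% power and 420 per arm. The main-trial alpha is not stated, so I assume 0.05 two-sided. With pooled variance and mean proportion 0.255:

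n = [1.960 × √(2 × 0.255 × 0.745) + 1.036 × √(0.30 × 0.70 + 0.21 × 0.79)]² / 0.09² = 420 per arm.

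With 30% attrition, 420 / 0.70 = 600 per arm, or 1200 in total. The plan's figures reproduce. They belong to the combined outcome.

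**Step 5. Illustration if only MDE were collected.** The documents give no MDE-only rate, so the control rates below are assumptions. The 30% relative reduction and the normal approximation are kept.

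| Assumed MDE-only control rate | Power at 420 per arm | n per arm for 85% power |
|---|---|---|
| 30% (as planned for CMD) | 85% | 420 |
| 25% | 76% | 533 |
| 20% | 64% | 703 |
| 15% | 50% | 985 |
| 10% | 34% | 1551 |

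These are not estimates of what would happen. If nearly every case also had MDE, little power would be lost. What would change in every row is the outcome being measured.

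**The case against.** The best reply is that the text already settles both instrument and visit. The analysis section names the SCID for both disorders, and the design and follow-up sections place the primary endpoint at six weeks. That stands. A reader of Table 4 might infer that GAD has no planned assessment at all, and the documents do not support that. The defect is an omission in the table that conflicts with the text. GAD data would be missing only if staff followed the table and not the text.

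Three other stronger inferences also fail.

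- **Screening.** The eligibility text names only "the depression component of the Structured Clinical Interview for DSM-5 (SCID", which might suggest that no GAD module is in use. That module is there to apply the MDE exclusion. GAD is not an exclusion, so its absence from eligibility screening says nothing about the six-week interview.
- **Half the endpoint.** No split of cases between GAD and MDE is given, so the share at risk is unknown. The 30% is labelled a rate for both disorders but is justified mainly by estimates of prenatal depression.
- **Symptom duration.** One might argue that a minimum-duration rule for GAD would stop the six-week diagnosis from capturing new postpartum onset. The documents state no such rule, so nothing can be built on it.

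A further objection is that the table may not be reliable as read. Other rows also disagree with the text. Blood draws are marked at screening, baseline and second trimester but not third, and the social support, relationship and disability scales sit in different columns from the narrative. Shifted columns could explain displaced marks, but they would not remove a row label. A row lost in extraction cannot be fully excluded. Table 4's note also refers to section 8.2.3 for descriptions of the tools, which is not in the supplied text and might say more about the SCID.

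**Conclusion.** The point holds as a contradiction between Table 4 and the endpoint definition. The text requires a SCID diagnosis of GAD at six weeks, while the schedule lists only the SCID diagnosis of MDE and has no GAD diagnosis row at any visit. No other scheduled measure substitutes for it. If staff work from the table, the GAD component of the primary outcome is not collected, and the loss in cases and power cannot be sized from the documents. The power figures above rest on assumed MDE-only rates and an assumed two-sided alpha of 0.05.

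Separately, the change-in-cases analysis cannot be carried out for GAD, because no GAD diagnosis is described before randomisation.

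The first conclusion assumes that the table as supplied is complete. If the full document holds a GAD row, only the baseline part may remain. The stated sample size is not in error.

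**What to change.** 1. Check the source table, section 8.2.3 and the six-week forms in use for a SCID GAD module.
2. If it is absent, add a row to Table 4 for a SCID diagnosis of GAD at six weeks for all randomised women, and put the GAD module in the assessment forms and assessor training.
3. Reword the primary analysis as a comparison of six-week prevalence of GAD or MDE between arms, which matches the primary objective. The alternative is to schedule the GAD module at baseline as well. The plan reads as a trial that has already enrolled women and is resuming, so a baseline module might cover only later entrants. The rewording applies to everyone.

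The cost is one table row, one form module, some assessor training and added interview time at a visit already planned for 1 to 1.5 hours. The documents do not say how long the module takes. The rewording costs a sentence and needs no new data. A baseline module would add interview time there too.

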#### Analysis of Primary Efficacy Endpoint(s)

The primary outcome of the study is the prevalence of cases of CMDs (GAD and MDE) in both study arms. Diagnosed cases of both GAD and MDE will be assessed with the Structured Clinical Interview for DSM Disorders (SCID).

The intervention group (enrolled after being screened for subclinical or clinical levels of anxiety) will be compared with non-intervention controls (selected on the same criteria) to examine the effects of the intervention on development of CMDs. The primary analysis will involve comparing pre- to post- changes in cases of the mothers randomly assigned to the two conditions using Fisher's exact test. Primary analyses will be non-parametric tests, however sensitivity analyses will use parametric models such as linear and logistic regression to control for baseline values of the mothers' characteristics (132). Other sensitivity analyses may evaluate whether there was more of an effect among women who got the full intervention. Variable transformations (such as square root or log) will be utilized as appropriate to meet the model assumptions.

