## Missing Data

Adjusted analysis and subgroup analysis will be based on covariates at baseline without non-missing values. Sensitivity analysis will be performed on the covariates with missing values imputed (133). Detailed imputation methods will be described in the statistical analysis plan. All analyses will be detailed in the statistical analysis plan, which will be finalized before un-blinding the study.

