## Baseline Descriptive Statistics

Regarding quantitative data, we will implement reliability and quality control checks, including randomly selected reliability checks on administration (in real time so corrections can be made, not compromising data quality) and scoring/coding of all measures within one week for completeness and accuracy. All questionnaires completed by trained assessment team members will be reviewed for skipped items or ambiguous answers; assessment team members will be asked to correct any missing or ambiguous entries. Data will be double entered. Data files will be checked with software for discrepancies, flagged and corrected. Although we will attempt to minimize the effects of missing data, some data will likely be missing due to maternal non-response at particular time points. Analyses will be conducted to examine the prevalence and patterns of missing data and methods appropriate for dealing with missing data (such as multiple imputation) will be used. All analyses will use an intent-to-treat (ITT) approach, using all subjects randomly assigned to treatment or control groups. Exploratory analyses will investigate whether effects are larger among mothers who participated in more intervention sessions (estimating complier average causal effects)(136). We will also do preliminary analyses to ensure that the randomization succeeded in creating similar groups at baseline. Baseline variables that are distributed unequally between the intervention and control groups will be adjusted for in the parametric models (below). Finally, to document a data collector effects, we will calculate inter-rater reliability (IRR) during the training period and calculate the Intra-class Correlation Coefficient (ICC) to measure differences between data collectors.

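### The primary Fisher's exact test leaves the screening HADS scores unused; covariates should be named in advance and the missing-outcome handling tied to the primary analysis

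*Combined protocol and SAP*

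**What the plan says.** The primary outcome is CMD (GAD and MDE, by SCID) at six weeks postpartum. Analysis of Primary Efficacy Endpoint(s) describes the main comparison as one of "changes in cases of the mothers randomly assigned to the two conditions using Fisher's exact test". I read this as a comparison of the two arms' proportions of cases at six weeks. Regression comes second: "Primary analyses will be non-parametric tests, however sensitivity analyses will use parametric models such as linear and logistic regression to control for baseline values". The baseline values are not named.

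Two further statements govern the regressions. Analysis of Secondary Efficacy Endpoint(s) says, for primary and secondary endpoints alike, that "in all regression models the coefficient on the HMHB vs. non-HMHB (control group) indicator variable will be taken as the estimated effect". Baseline Descriptive Statistics says: "Baseline variables that are distributed unequally between the intervention and control groups will be adjusted for in the parametric models". It gives no list and no threshold.

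The HADS is part of screening (section IV; Screening Procedures), and Table 4 schedules both subscales there. A HADS-anxiety score of at least 8 is an entry criterion. No analysis of the primary endpoint names either score as a covariate.

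On missing data, the Missing Data paragraph deals with covariates ("Sensitivity analysis will be performed on the covariates with missing values imputed") and leaves imputation detail to a statistical analysis plan to be completed before un-blinding. Baseline Descriptive Statistics expects that "some data will likely be missing due to maternal non-response at particular time points", promises that "methods appropriate for dealing with missing data (such as multiple imputation) will be used", and commits to intention-to-treat, "using all subjects randomly assigned to treatment or control groups". Section III.B allows for 30% attrition.

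**The concern.** The Background ranks prenatal anxiety among the strongest predictors of postpartum CMD, and the mixed models of the biological substudy adjust for baseline severity. The primary endpoint, where precision matters most, gets no such adjustment although the scores are already collected.

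Choosing covariates by observed imbalance makes the sensitivity models depend on the data. A variable's value as a covariate lies in how well it predicts the outcome, not in how it happens to fall between arms. In a logistic model the arm coefficient also changes meaning with the covariates included, so a data-driven list leaves the estimated quantity unfixed.

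For missing outcomes there is a principle but no link to the primary test. Nothing says whether a missing six-week SCID is dropped from Fisher's test or imputed. The listed reasons for withdrawal include psychiatric illness leading to admission, so loss related to the outcome is plausible. Imputation under missing at random does not remove bias from such loss, and only a sensitivity analysis shows how far the result depends on it.

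**Working it through.** **Inputs.** From section III.B: CMD 30% in controls, a 30% relative reduction (0.30 × 0.70 = 21%), 85% power, 420 per arm evaluable, 30% attrition, 600 per arm enrolled. Alpha is not stated for the main trial; two-sided 0.05 is assumed.

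**1. The plan's own figure.** Pooled two-proportion formula, mean proportion 0.255:

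n = [1.960 × √(2 × 0.255 × 0.745) + 1.036 × √(0.30 × 0.70 + 0.21 × 0.79)]² / 0.09² = (1.208 + 0.635)² / 0.0081 ≈ 420 per arm.

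420 / 0.70 = 600 enrolled, so 180 per arm are expected without an outcome. Both planned figures reproduce.

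**2. Fisher's test at that size.** Full enumeration at 420 per arm gives power 83.3% and actual size 4.2% (at 30% in both arms).

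**3. Logistic regression and HADS adjustment.** The documents give no HADS–CMD association among eligible women, so the odds ratios below are assumptions. Simulated power at 420 per arm, 30% versus 21%, 10,000 trials per row, one normal covariate:

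| Odds ratio per SD (eligible women) | Unadjusted logistic | Adjusted | Gain, points |
|---|---|---|---|
| 1.0 | 84.8% | 84.6% | about 0 |
| 1.25 | 85.2% | 85.5% | 0.3 |
| 1.5 | 85.0% | 86.4% | 1.4 |
| 2.0 | 85.5% | 88.4% | 2.9 |
| 2.5 | 84.4% | 89.2% | 4.8 |

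Unadjusted logistic regression is at about 85%, roughly 2 points above Fisher's 83.3%. HADS adds 0 to 5 beyond that.

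The entry cut-off narrows the HADS-anxiety range. Suppose the 35% to 49% anxiety prevalence in the Background is the share at or above the cut-off and scores are normal (both assumptions). The SD among eligible women is then 0.54 to 0.60 of the population SD. A population odds ratio of 2.0 per SD becomes 2.0^0.536 = 1.45 to 2.0^0.598 = 1.51, and the gain is 1.3 to 1.4 points (2.7 to 3.1 at a population odds ratio of 3.0). Using both HADS scores (correlation 0.5, odds ratios from 1.25 and 1.25 up to 1.5 and 2.0) adds about 1 to 4 points. The size of the two-covariate model at 30% in both arms was 4.7% to 5.1%.

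**4. What the arm coefficient means.** Unadjusted odds ratio: (0.21/0.79) / (0.30/0.70) = 0.620. With both scores in the model, for the same 30% versus 21%, it is 0.612, 0.594 or 0.574 (odds ratios 1.25/1.25, 1.5/1.5, 1.5/2.0). A standardised risk difference does not drift in this way.

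**5. Missing outcomes.** Take 126/420 versus 88/420 observed.

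- Complete case: p = 0.003.
- Missing counted as non-case, 126/600 versus 88/600: p = 0.005.
- Missing counted as case, 306/600 versus 268/600: p = 0.032.

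For a tipping point, let missing women differ from observed women by δ_H (HMHB) and δ_C (control). Since 180/600 = 0.30,

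difference over all randomised = 0.09 − 0.30 × (δ_H − δ_C).

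SE from the observed women: √(0.30 × 0.70/420 + 0.21 × 0.79/420) = 0.0299, so significance needs a difference of 1.96 × 0.0299 = 0.0586. With δ_C = 0 this is lost at δ_H = (0.0900 − 0.0586)/0.30 ≈ 10.5 points. With multiple-imputation variance, p is 0.049 at 10 points (difference 6.0 points) and 0.056 at 10.5. If both arms shift equally, the difference stays at 9.0 points.

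**The case against.** The strongest reply is that nothing here is invalid. Fisher's test controls error, randomisation is not described as stratified by HADS, the sample size reproduces, and about 2 of the points gained come from leaving Fisher's test rather than from HADS. The rest depends on assumed associations, and the entry cut-off keeps it small. The section answers a request for a brief analysis plan and defers detail. Changing a prespecified primary test in a running trial also has a price. All of this stands, and it limits the size of the point. It does not remove the case for using scores already collected or for naming covariates beforehand.

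Four stronger readings are tempting, and the documents do not support them.

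- *There is no rule for missing outcomes.* Baseline Descriptive Statistics commits to intention-to-treat and to methods such as multiple imputation, and Missing Data defers detail to a later plan. What is absent is the link to the primary test and, in these documents, a missing-not-at-random check. The later plan may supply both.
- *The primary test is adjusted by observed imbalance.* That rule concerns only the parametric sensitivity models, and may add to the baseline values mentioned under the primary endpoint rather than replace them.
- *HADS would almost never enter.* Under a p<0.05 imbalance threshold applied as the sole rule, at least one HADS score enters in about 9% of simulated trials. The documents state neither the threshold nor the exclusivity.
- *Missing data will produce false positives.* With no true effect and HMHB cases alone lost at 40%, Fisher's test rejects about 26% to 28% of the time and imputation by arm 24% to 29%. With cases lost at 40% in both arms, Fisher's test rejects 3.9%. The inflation belongs to one-arm loss, which the documents do not predict.

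**Conclusion.** The point holds as an improvement in efficiency and prespecification, not as an error. The primary test is valid and slightly conservative: 83.3% power and 4.2% size at 420 per arm, two-sided 0.05 assumed. Leaving out HADS costs precision only. Logistic regression recovers about 2 points of power and HADS adjustment roughly 0 to 5 more, the latter resting on odds ratios that the documents do not give. The imbalance rule leaves the sensitivity estimates open to the data.

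The missing-outcome part supports the point but would not carry it alone, since detail is deferred. The 10-point tipping margin is an illustration: it takes the planned 30% versus 21% among observed women and holds missing controls at their observed rate. All three simple treatments of missing outcomes remain significant at that effect.

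**What to change.** Before un-blinding:

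1. Make the primary analysis a logistic model of six-week CMD on arm, adjusted for continuous screening HADS-anxiety and HADS-depression, both named in advance. Report the standardised risk difference and risk ratio with 95% confidence intervals. Keep Fisher's exact test as a sensitivity analysis.
2. Replace the imbalance rule in Baseline Descriptive Statistics with that fixed covariate list.
3. In the statistical analysis plan, apply multiple imputation by arm to the missing six-week CMD outcome. Use baseline measures and, where observed, the third-trimester ones (PES-Brief, perceived stress, social support, functional disability); women lost before that visit will not have the latter. Add a delta-adjusted tipping-point analysis that varies the shift in each arm separately.

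The data are already scheduled for collection, so the work is an amendment to the research plan, text in the analysis plan and modest programming. The real costs are a model-based estimate in place of an exact test, and an amendment to a prespecified primary test in a trial already under way. The date and reason of the amendment should therefore be recorded while allocation is still masked.
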